# 7.1 TUS-related complication definitions:

Complications are defined as occurring in first 3 months post transplant except transplant ureteric stenosis which can develop insidiously and so will be recorded for the first 6 months post transplant.

- Urinary Tract Infection (UTI) microbiology (MC&S) in the early (<3month) post transplant setting
  - Symptomatic dysuria / fever / pain over transplant or native kidneys with Mid Stream Urine (MSU) culture bacteria  $> 10^{x^2}$  with pyuria
  - Asymptomatic Mid Stream Urine (MSU) culture bacteria  $> 10^{x5}$  with pyuria
- Stent migration ultrasound and / or plain x-ray diagnosis of TUS not appropriately positioned (coils not in both the transplant renal pelvis and the bladder).
- Stent pain requiring stent removal
- Haematuria frank haematuria requiring catheterisation +/- irrigation
- Stent Fragmentation

#### **Urological complications definitions:**

- "Urinary leak "- Transplant Uretero-neocystotomy anastomotic leak diagnosed by biochemical confirmation (creatinine level of transplant drain fluid); radiological evidence on cystogram; intra-operative assessment with intravesical methylene blue testing.
- Transplant ureteric stenosis diagnosed with radiological evidence using antegrade nephrostogram (pyelo-ureterogram).

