|  | 3. Simultaneous Kidney and Pancreas
Transplant (SPK)  |
| Investigational medicinal product and dosage             | N/A; this is not a trial of an investigational medical product   |
| Active comparator product(s)                             | N/A  |
| Route(s) of administration                               | N/A  |
| Maximum duration of treatment of a subject               | N/A  |
| Procedures: Screening & enrolment                        | All patients undergoing kidney
transplantation will be considered for
enrolment  |
| Baseline   | Baseline recipient data will be recorded.  |
| Treatment period
End of Study                         | The intervention is non-pharmacological.
Patients will be randomised to one of two
groups: control (conventional cystoscopic
TUS removal) or trial (new method with early
TUS removal), refer to flow diagram. Trial
group will have their TUS attached to their
catheter during surgery. Both Catheter and
TUS will be removed on day 5 post surgery.
The control arm will undergo catheter
removal on day 5 and the current
conventional method of cystoscopic TUS
removal at week 6.
Follow-up visits and tests are part of the
transplantation protocol in the centres. Data
will be obtained from the medical notes and
local centre databases for up to 1 year
Patients will be followed-up for 1 year |
| Procedures for safety monitoring                         | Complications will be reported to the Data   |
| during trial   | Safety Monitoring Committee (DMC). The   |
|  | committee will meet in the $1^{st}$ month & then at 3 monthly intervals.   |
| Criteria for withdrawal of patients on
safety grounds | 
 
An increased rate of stent related
complications in the eTUSr arm (>20%)
 
An increase in ureteric complications in
the eTUSr arm (>1% urinary leak or >2
cases in the 1st month; 20% ureteric
stenosis or >3 cases at 3 months)
 
Clinically and statistically different
outcomes are shown in either arm and
continuation of the study is considered
unethical
 
  |
| Regulatory submissions on safety grounds                 | Not required as not a CTIMP  |

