#### 8.2 Potential risks

There is the potential for unexpected complications in the new technique arm of the study. These may be related to the early removal of the stent on the 5th post operative day.

- The main potential complication is an increase in the urinary leak rate (>1%). This would be clinically detectable by a decrease in voided urine volume and discomfort around the transplanted kidney. Investigation would be with an ultrasound scan. Treatment would be with replacement of the urinary catheter for 2 weeks and a cystogram before removal. Any incident of urinary leak in either group would be immediately reported to the Trial Data Safety Monitoring Committee. An increase incidence in urinary leak rates (>2 cases in the first month) in either arm would trigger a trial safety review and if necessary temporary cessation in the study until appropriate clinical review. However, data to date from the literature  and personal communications (The Mayo Clinic, 2006) suggest no increase in urinary leak complication rate with the new technique.
- There is the potential that we find an increase rate (>15-20%) of ureteric stenosis in the early (3 month) post transplant period. This would present with a decrease in void volume, discomfort around the transplant or deteriorating renal function.

Investigation would involve an ultrasound scan and be initially managed with either nephrostomy or retrograde insertion of ureteric stent. Nephrostogram / retrograde x-ray would be obtained to confirm diagnosis. Treatment would involve either endo-urological or an open corrective surgical approach. >3 cases of stenosis in the first 3 months would generate trial review. Data to date does not suggest increased complications of stenosis with early removal of ureteric stents.

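### The stenosis endpoint in section 7.1 accepts only an antegrade study, while section 8.2 also allows retrograde confirmation, so cases can go uncounted

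*Protocol*

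**What the plan says.** **Stenosis.** The urological definitions in Protocol section 7.1 give one criterion: "Transplant ureteric stenosis diagnosed with radiological evidence using antegrade nephrostogram (pyelo-ureterogram". Section 8.2 describes what happens when stenosis is suspected. After an ultrasound scan, initial management is by "nephrostomy or retrograde insertion of ureteric stent", and then "Nephrostogram / retrograde x-ray would be obtained to confirm diagnosis".

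**Leak.** Section 7.1 lists three routes. A leak is "diagnosed by biochemical confirmation (creatinine level of transplant drain fluid"), or there is "radiological evidence on cystogram; intra-operative assessment with intravesical methylene blue testing". It does not say whether any one of these suffices. Section 8.2 says of a suspected leak: "Investigation would be with an ultrasound scan. Treatment would be with replacement of the urinary catheter for 2 weeks and a cystogram before removal".

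**Where the counts are used.** Section 5.8 makes leak at 3 months and stenosis at 6 months secondary endpoints for each arm. Section 8.2 calls for a trial review if there are more than 3 stenoses in the first 3 months. Section 8.4 includes more than 3 cases at 3 months in the eTUSr arm among its stopping conditions. Neither section gives a case definition of its own.

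**The concern.** Section 8.2 treats a retrograde x-ray as confirming a stenosis, but section 7.1 does not count one on that evidence. A patient handled by the retrograde route can thus have a stenosis that the trial regards as confirmed and that never enters the endpoint. Stenosis is one of the two ureteric harms that the protocol itself raises for early stent removal. It is also monitored against a small absolute count, where one or two cases matter. Anyone applying 7.1 literally would under-count. Anyone applying 8.2 would count more, and two centres could classify the same patient differently.

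The leak definition has a narrower form of the same problem. Ultrasound is the investigation named in 8.2 but is not a criterion in 7.1, and the cystogram is placed after two weeks of treatment.

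**Working it through.** **1. Stenosis: the two sections side by side.**

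| Pathway under 8.2 | Confirming image | Counted under 7.1? |
|---|---|---|
| Nephrostomy | Nephrostogram (antegrade) | Yes |
| Retrograde stent insertion | Retrograde x-ray only | No |
| Retrograde stent insertion, antegrade study also done | Both | Yes |

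This reads the slash in 8.2 as *or*. The sentence before it supports that reading, because it offers nephrostomy and retrograde stenting as alternatives. The second row is the gap.

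**2. Leak: the two sections side by side.**

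| Test | Criterion in 7.1? | Mentioned for leak in 8.2? |
|---|---|---|
| Drain-fluid creatinine | Yes | No |
| Cystogram | Yes | Yes, but after 2 weeks of catheter |
| Intra-operative methylene blue | Yes | No |
| Ultrasound | No | Yes, as the investigation |

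Cystogram is common to both sections, so they do not contradict each other outright. A case escapes 7.1 only if all three of these hold: it was suspected on ultrasound, it had healed by the 2-week cystogram, and it had no positive drain-fluid creatinine or methylene blue test.

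**3. Size for stenosis (illustration only).** The documents state no stenosis rate and no share confirmed by the retrograde route alone, so both are assumed. The number per group, 88, is from section 5.5. Let *r* be the true risk and *f* the retrograde-only share.

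Expected counted cases = 88 × *r* × (1 − *f*).

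| Assumed *r* | True expected cases | *f* = 10% | *f* = 25% | *f* = 50% |
|---|---|---|---|---|
| 2% | 88 × 0.02 = 1.76 | 1.58 | 1.32 | 0.88 |
| 5% | 88 × 0.05 = 4.40 | 3.96 | 3.30 | 2.20 |
| 10% | 88 × 0.10 = 8.80 | 7.92 | 6.60 | 4.40 |

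**4. Effect on a count of more than 3 (illustration only).** Suppose the trigger uses the 7.1 definition, *r* is the risk by 3 months, and all 88 eTUSr patients contribute. The counted number is then binomial with size 88 and probability *r*(1 − *f*). For *r* = 5%, the chance that it exceeds 3 is:

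- *f* = 0: probability 0.05, chance 65%
- *f* = 10%: probability 0.045, chance 56%
- *f* = 25%: probability 0.0375, chance 42%
- *f* = 50%: probability 0.025, chance 18%

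**5. Effect on the comparison of arms.** If *f* is the same in both arms, the ratio of counted risks is *r*₁(1 − *f*) / *r*₀(1 − *f*) = *r*₁/*r*₀, which is unchanged. The difference becomes (*r*₁ − *r*₀)(1 − *f*), so the absolute excess is understated by the share *f*. The ratio is distorted only if *f* differs between arms, and the documents give no information on that.

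**The case against.** The strongest reply is that section 8.2 is a risk narrative in the ethics part of the protocol, not an endpoint specification. It does not say that an antegrade study, a drain-fluid creatinine or a methylene blue test will be omitted, so in practice every case might meet 7.1. The link to the safety limits is also loose. Section 8.2 has any leak reported immediately to the monitoring committee, section 8.4 leaves stopping to the committee's opinion, and neither ties reporting to the 7.1 criteria. These points stand as limits on size: the under-count is possible, of unknown frequency, and may not reach the committee's decisions. They do not remove the conflict for stenosis, because 8.2 names retrograde imaging as confirmation and 7.1 leaves it out.

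A reader might infer three stronger things, which the documents do not support.

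- **That 7.1 rejects the leak work-up in 8.2 altogether.** It does not. Cystogram appears in both, and only the narrow case in step 2 of the working is affected.
- **That the 6-month window miscounts stenosis, because controls keep the stent for 6 weeks.** The arithmetic is right: taking 6 months as 183 days, stent-free time is 183 − 5 = 178 days against 183 − 42 = 141. But a common window from transplant is a valid randomised comparison of two strategies. Any cut-off of late control cases would make early removal look worse, not hide its harm. The 3-month stopping count in 8.4 concerns the eTUSr arm alone, so control stent-free time does not enter it.
- **That the planned Mantel-Haenszel test is a defect here.** Adding risk differences with exact intervals is a choice for the statistical analysis plan, which is not shown, and has no bearing on the definitions.

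It is also fair to object that counting every treated leak would put clinical judgement in place of objective criteria in an unblinded trial. That objection stands, and it shapes the fix.

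**Conclusion.** The point holds for stenosis. Sections 7.1 and 8.2 disagree on what confirms one. Followed as written, 7.1 omits a case confirmed only by the retrograde route from the 6-month secondary endpoint, and possibly from the more-than-3-cases trigger. The effect on the trigger is conditional on the committee using the 7.1 definition.

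The size is unknown. The figures in the working rest on an assumed risk, an assumed retrograde-only share and 88 patients in the arm. They show that a modest share could matter against a limit of 3, not that it will. The documents give no ground for expecting the share to differ between arms, so a biased comparison is not shown.

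The leak gap is real but smaller, and depends on a specific sequence of events. A conclusion that the main harms of early removal are miscounted would go beyond the evidence; what the documents support is that they can be under-counted, mainly stenosis. This is a wording correction to a secondary safety endpoint and does not touch the primary comparison.

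**What to change.** Reconcile sections 7.1 and 8.2 for counting purposes. Reword 7.1 so that a stenosis counts when confirmed by either imaging route named in 8.2, and record on the case report form which route was used. State in 8.2 and 8.4 that the stenosis trigger uses this same definition. None of this alters how a patient is investigated or treated.

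For leak, keep the objective 7.1 criteria for the main analysis and say whether any one of them is enough. Record a leak suspected on ultrasound and managed as a leak, but meeting no 7.1 criterion, as probable, and report these by arm in a separate sensitivity count.

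The cost is a few lines of endpoint wording and two added fields on the case report form. The probable category is less certain and open to judgement in an unblinded trial, which is why it should stay out of the main count.

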#### 7.2 Follow-up schedules and requirements

Patients in the eTUSr group who have urethral catheter / stent removed earlier or later than Day 5 post operation will have the reason clearly documented in medical notes. The post-operative day urethral catheter / stent removed will be clearly recorded. Patients in the sTUSr group will have the TUS removed in week 6 post transplant. Patients who have TUS-related complications that warrant TUS removal before 6 weeks will have the reason clearly documented in medical notes. The post-operative day the TUS is removed will be clearly recorded. If for administrative reasons (such as availability of cystoscopy list) TUS removal is earlier or later than 6 weeks the reason clearly documented in medical notes.

Urine samples will be collected routinely (current clinical practice) as follows:

- At admission for transplant: in patients who pass urine MSU for MC&S (microscopy, culture and sensitivity)
- Prior to urethral catheter removal day 5 CSU (catheter specimen urine) for MC&S
- At each transplant outpatient clinic midstream urine samples are dipstick tested. Abnormal results on dipstick test are sent for MC&S. Month 1: 3 visits/ week; Month 2: 2 visits/ week; Month 3: 1 visit / week.

• Prior to cystoscopic removal of TUS - MSU for dipstick and MC&S (microscopy, culture and sensitivity)

Health economics:

- Assessment of costs of eTUSr versus sTUSr.
  - Hospital costs assessed by NHS reference costs.
  - Patient costs by self-completed diary cards and will include both direct costs (expenditure) and indirect costs (e.g. loss income).

Patient satisfaction:

• Quality of Life assessment (using FAIT-U, version 4.0 and EQ -5D) will be carried out by adult participants in both treatment arms.

# 8. ETHICAL CONSIDERATIONS

# 8.1 Potential Benefits

Kidney transplantation is the most economic form of renal replacement therapy and compared to dialysis is the preferred treatment for most patients. However, there are side-effects and potential complications related to transplantation. It is important to direct our efforts to minimise them. This study aims to address specific post-operative urinary tract complications including infection associated with the routine use of transplant ureteric stents.

The potential value of this research will be to determine which approach has:

- Lowest urinary tract infection rates
- Lowest urinary tract complication rates
- Better patient acceptability
- Better cost effectiveness (health economic outcome)

#### 8.2 Potential risks

There is the potential for unexpected complications in the new technique arm of the study. These may be related to the early removal of the stent on the 5th post operative day.

- The main potential complication is an increase in the urinary leak rate (>1%). This would be clinically detectable by a decrease in voided urine volume and discomfort around the transplanted kidney. Investigation would be with an ultrasound scan. Treatment would be with replacement of the urinary catheter for 2 weeks and a cystogram before removal. Any incident of urinary leak in either group would be immediately reported to the Trial Data Safety Monitoring Committee. An increase incidence in urinary leak rates (>2 cases in the first month) in either arm would trigger a trial safety review and if necessary temporary cessation in the study until appropriate clinical review. However, data to date from the literature  and personal communications (The Mayo Clinic, 2006) suggest no increase in urinary leak complication rate with the new technique.
- There is the potential that we find an increase rate (>15-20%) of ureteric stenosis in the early (3 month) post transplant period. This would present with a decrease in void volume, discomfort around the transplant or deteriorating renal function.

Investigation would involve an ultrasound scan and be initially managed with either nephrostomy or retrograde insertion of ureteric stent. Nephrostogram / retrograde x-ray would be obtained to confirm diagnosis. Treatment would involve either endo-urological or an open corrective surgical approach. >3 cases of stenosis in the first 3 months would generate trial review. Data to date does not suggest increased complications of stenosis with early removal of ureteric stents.

• There is the potential for a short increase in the operating time during kidney transplant surgery. We anticipate that the new technique of suturing the stent to the catheter will add between 5 to 10 minutes to the overall surgery time of approximately 3 hours (however this can vary between 2-6 hours depending on complexity of case). Operating time data is routinely collected from all surgery (Galaxy System). Any unforeseen problems will be notified to the Trial Data Safety Monitoring Committee. Mean operating times over 3 monthly periods will be assessed between trial groups. A significant increase (> 1 hour) difference in mean operating times would trigger a trial safety review and if necessary temporary cessation in the study until appropriate clinical review.

This study has been reviewed and given favourable opinion by Guy's Hospital Research Ethics Committee and additionally has been passed by the Renal Project Board of Guy's Hospital.

We will ensure that our participants are fully informed of the potential risks and benefits before they are able to enter the trial. Trial information will be given at pre-transplant education sessions by both a researcher and a member of the direct care team. Information leaflets will be provided and are adapted to individual age groups. Adequate time to consider the information and ask questions before making a decision will be given to all potential participants.

# 8.3 Data Protection

All data collected in the study will be anonymised and stored on a password protected computer or on password protected memory sticks. All data will be stored and archived within the Guy's and St Thomas' renal transplant department archive in line with the Joint Clinical Trials Archiving recommendations.

# 8.4 Data Monitoring Committee

There will be not be a separate Trial Steering Committee, but the Trial will be overseen by the Data Monitoring Committee below.

*Committee Chair:* [name] (Consultant in Nephrology, GSTT) *Members:* [name] (Consultant in Renal Transplantation, GSTT and coapplicant) [name] (Consultant in Urology, GSTT); [name] (Head of Clinical Governance GSTT Renal Department); [name] (Consultant in Renal Transplantation GSTT and lead applicant); [name] (Consultant Paediatric Nephrologist, Evelina Children's Hospital, GSTT); [name] (Professor of Medical Statistics, King's College London), [name] (Research Fellow in Biostatistics and Bioinformatics, MRC centre for transplantation); [name] (Clinical Research Fellow in Urology, GSTT). The committee will assess trial progress, occurrence of adverse events and other aspects of the trial such as recruitment. The committee will meet in the 1st month & then at 3 monthly intervals.

The trial will be stopped if in the opinion of the Data Monitoring Committee the following conditions have been satisfied:

An increase rate of stent related complications in the eTUSr arm (>20%) An increase in ureteric complications in the eTUSr arm (>1% urinary leak or >2 cases in the 1st month; 20% ureteric stenosis or >3 cases at 3 months) Clinically and statistically different outcomes are shown in either arm and continuation of the study is considered unethical.

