#### 5.5 Sample Size Determination

An audit over the last 3 years has demonstrated that between 15 to 20% of patients have TUS-related complications, mainly UTI in the first 3 months post transplant surgery. On this basis, we aim to reduce our TUS-related complication rate to a target rate of 5%. Statistical power calculations were performed by [name], Statistician, KCL, London. Based on a chi-squared test with 80% Power and a 5% 2-sided type I error rate 88 patients per group are required assuming a current 20% TUS-related complication rate. The corresponding number is 160 patients per group assuming a current 15% TUS-related complication rate.

As there is a degree of uncertainty in the starting TUS-related complication rate, we will perform a sample size re-estimation based on predictive power after 25 patients per group which we anticipate will be 3 months into the trial.

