# 5.9 Trial Treatments

The study is a randomised control trial in which there are two potential study arms to which patients are randomly allocated, see below. It is not possible to blind patients or investigators as to whether they will undergo the standard technique or the novel technique for stent removal due to noticeable differences in the method of procedure.

*Group 1*: CONTROL - Standard technique for TUS removal (sTUSr) *Group 2*: TRIAL - Novel technique with early TUS removal (eTUSr)

A TUS is placed at the time of surgery along with a urinary catheter in all patients. Patients in Group 1 will have the urinary catheter removed on the ward on the 5th post-operative day. They will then undergo a cystoscopy, under either local or general anaesthetic, at week 6 to remove the TUS. Cystoscopy and stent removal takes

approximately 10 minutes. Patients will be given a prophylactic intravenous injection of antibiotic to cover the procedure. Patients in Group 2 will have the TUS attached to the urinary catheter at the time of surgery. These patients will have the urinary catheter removed on the ward on the 5th post-operative day in the standard way. As the TUS is attached to the catheter it will be removed at the same time as removal of the catheter. Catheter removal simply involves deflating the catheter balloon to allow it to slide out from the bladder. It is a non-invasive procedure that does not cause discomfort or risk to the patient. Removing the catheter with the stent attached will not change this. Group 2 therefore do not require cystoscopy.

The study will be performed prospectively. Patients that require kidney transplantation will be recruited and allocated to a study arm. Participants of the study will have routine clinical follow up in the same way as non-participants. A diary card will be completed by both trial groups on the day of their stent removal. Stent related symptom assessment and quality of life questionnaires will be completed by all adult participants at week 1 and week 6. Data will be collected on all participants regarding ureteric complications, stent related complications, health economics and patient quality of life assessments for 3 months post transplantation. Complications of ureteric stenosis will monitored for up to 6 months post transplantation.

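### Section 8.4 seats the lead applicant and a co-applicant on the only committee that reviews outcomes by arm and decides on stopping, in an open-label trial with no stated closed session

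*Protocol*

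**What the plan says.** Section 8.4 sets out the oversight structure: "There will be not be a separate Trial Steering Committee, but the Trial will be overseen by the Data Monitoring Committee below". It lists a chair and eight members. Among them are the "Consultant in Renal Transplantation GSTT and lead applicant" and a "Consultant in Renal Transplantation, GSTT and coapplicant", together with a clinical research fellow in urology at the same trust. The synopsis names that trust as the sponsor. Meetings are in the first month and every 3 months after that.

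The same section gives the committee its authority: "The trial will be stopped if in the opinion of the Data Monitoring Committee the following conditions have been satisfied". The conditions include "An increase rate of stent related complications in the eTUSr arm (>20" (the figure is a percentage), limits on leak and stenosis in that arm, and "Clinically and statistically different outcomes are shown in either arm and continuation of the study is considered unethical".

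Two other sections bear on the point. Section 5.9 states that the trial is open-label: "It is not possible to blind patients or investigators as to whether they will undergo the standard technique or the novel technique". Section 5.5 adds an interim calculation: "we will perform a sample size re-estimation based on predictive power after 25 patients per group". It does not say who sees the data for that calculation.

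**The concern.** A monitoring committee is meant to keep the accumulating comparison away from those who recruit, treat and record outcomes, and to judge harm without a stake in the answer. Here the people who proposed the trial sit, without any stated restriction, on the body that does this.

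Lack of blinding makes the separation more important. Clinicians already know each patient's allocation, but they need not know the aggregate result. Someone who knows how the comparison is running may recruit differently or, without intending to, record borderline events differently. Analysis cannot remove such an effect afterwards. The decisions to stop, to continue, or to enlarge the trial from 176 to 320 patients (section 9) would also be shaped by people with an interest in the outcome.

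**Working it through.** No figure in the protocol is in dispute, so the check is mainly a reading of the sections side by side.

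**1. Membership (8.4).** Chair plus eight members = 9. Listed at the sponsor trust: the nephrologist chair, the two transplant consultants (lead applicant and co-applicant), the urologist, the clinical governance lead, the paediatric nephrologist and the urology research fellow = 7. The other two are a professor of medical statistics and a biostatistics research fellow, neither listed at the sponsor trust. Taking out the two applicants and the urology fellow leaves 9 − 3 = 6, of whom 4 are from the sponsor trust and 2 are the statisticians.

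**2. Do the stopping conditions need data by arm?**
- Complications above 20%: stated for the eTUSr arm.
- Leak and stenosis limits: stated for the eTUSr arm.
- Clinical and statistical difference: a comparison of the two arms.

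None of these can be judged from pooled data. Section 8.2 also has mean operating times compared between trial groups over 3-monthly periods. Arm-level access is therefore a consequence of the rules as written.

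**3. Is anyone excluded, or is there another body?** Section 8.4 mentions no open and closed sessions, recusal or non-voting status. Section 8.4.2 gives the Joint Clinical Trials Office Quality Team oversight of Good Clinical Practice and scientific integrity, and section 8.2 records ethics approval. Neither is given a role in reviewing outcomes or deciding on stopping.

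**4. How often?** Month 1 and then every 3 months gives months 1, 4, 7, 10, 13, 16, 19 and 22, which is 8 meetings within the 24 months that section 9 gives for recruiting 176 patients. The next falls at month 25. Eight is an upper limit for informative looks at the primary endpoint during recruitment: at month 1 nobody has completed the 3-month complication window of section 7.1.

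**5. The re-estimation (5.5).** It is due at 25 per group, that is 50 patients, expected at about 3 months. Predictive power normally uses the observed difference between arms, so it is a further route to the comparison. No firewall is stated.

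**6. Where could knowledge of the comparison act?** By section 7.1:
- UTI: recorded symptoms decide whether the culture limit is 10^2 or 10^5.
- Stent pain: counts only if the stent has to be removed for it.
- Haematuria: counts only if catheterisation is needed.

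These keep some clinical discretion. Migration rests on imaging. Urine sampling is largely fixed by section 7.2, with a dipstick at every clinic visit, culture of abnormal results, and culture before cystoscopy.

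**The case against.** The case on the other side has several parts.

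- **The documents do not say that the applicants vote.** A reader might infer a vote. The text speaks only of the committee's opinion and describes no procedure, and a charter or the unseen analysis plan might set one. This stands as to the word. It does not remove the point, because section 8.4 itself fixes the membership and the stopping authority and restricts no member.
- **Open-label treatment is the main source of bias, and the change would not remove it.** This largely stands. Clinicians will still know their own patients' allocation and outcomes. The change removes only the added influence of knowing the aggregate comparison.
- **Endpoint discretion is limited.** A reader might infer that sending urine for culture, or judging a ureter's vascularity, is an open route into the endpoint. Section 7.2 largely fixes the first. The second is an eligibility criterion in section 5.2 and not an endpoint component.
- **Fragile significance is not evidence of bias.** With 88 per arm, 12 v 4 events gives p = 0.036 by uncorrected chi-squared and 11 v 4 gives p = 0.059, so a reader might infer that committee membership could decide the result. Any binary trial is sensitive near its boundary. With continuity correction, 12 v 4 already gives p = 0.066, and section 7 plans a stratified Mantel-Haenszel test in any case. These figures do not measure the effect of membership.
- **The re-estimation may not expose the applicants.** Section 5.5 justifies it by uncertainty in the starting complication rate and says a statistician did the power calculations. Its use of the word 'we' does not show that the applicants would see arm-level data. This stands; what remains is that no separation is stated.
- **This is a non-CTIMP with ethics approval, a chair not identified as an applicant, and two statisticians listed outside the sponsor trust.** These are mitigating facts and bear on severity.

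**Conclusion.** The point holds as a badly fixed rule: the only body that reviews outcomes and decides on stopping includes the lead applicant, a co-applicant and a urology research fellow at the sponsor trust, and its criteria require results by arm. Exposure is up to 8 meetings during the stated 2-year recruitment, plus the re-estimation at 25 per group if predictive power is computed in the usual way.

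The size of any bias cannot be computed from the protocol. A reader might infer that the result will be biased, or that the trial cannot be relied on. The documents do not support that: they show an avoidable route for influence and not an effect.

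The conclusion assumes that listed members take full part, since nothing says otherwise, and that the urology fellow works on this trial, which the protocol does not state outright. It should be fixed, preferably before the first arm-level review because disclosure cannot be undone, but it does not by itself invalidate the design.

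**What to change.** Amend section 8.4 as follows, with a short committee charter.

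- The lead applicant, the co-applicant and the urology research fellow attend an open session only (recruitment and pooled data) and take no part in stopping decisions.
- The six other named members, including the two statisticians, hold a closed session on arm-level data and receive the results of the section 5.5 re-estimation.
- The closed session returns only a recommendation to stop, to continue or to change the sample size.
- Each closed-session member confirms that they do not classify trial outcomes.
- Individual leaks are still reported immediately, as section 8.2 requires.

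The cost is one amendment and a short charter. The applicants lose sight of interim results by arm. The closed group is smaller and still mainly from the sponsor trust (4 of 6). The protocol does not show which of the six treat trial patients or classify their outcomes. If the confirmations leave too few members, an outside member would be needed, so it should not be assumed that the change needs no new people.
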